Group A (n = 30) will receive only vaginal Misoprostol 800mcg (4 tablets Cytotec 200mcg)(Pfizer)every 3 hours to a maximum of two doses or until reaching cervical ripening.

(The doses of Misoprostol will follow the New FIGO Guidelines for Misoprostol use 2017)

Group B (n = 30) will receive combined vaginal Misoprostol 800mcg (4 tablets Cytotec 200mcg) every 3 hours to a maximum two doses with Isosorbide-5-

mononitrate 20 mg (Effox20 mg)(MINAFARM) once at the beginning with misoprostol(**Athanasios Mousiolis et al., 2012**)

- **Study setting:**

Embaba General Hospital Obstetrics and Gynaecology Department

- **Inclusion criteria:**

- Maternal Age 18 - 35 years.
- Gestational age first trimester of pregnancy (between 5-13 weeks).
- Missed abortion confirmed by ultrasound.
- Singleton pregnancy.
- Normal uterus and cervix on clinical examination.
- Cervix is not dilated.
- No vaginal bleeding.

- **Exclusion criteria:**

- Evidences suggesting start of spontaneous abortion and previous trial to induce abortion.
- Presence of uterine contraction or bleeding,
- Multi-fetal pregnancy.
- Suspicion of septic abortion.
- History of Previous cervical surgery or manipulation. Ex: cervical tear , cervical cauterization .
- Uterine anomaly.
- Presence of IUD in situ.
- Underlying medical diseases.Ex:DM,HTN
- History of allergy or adverse effects to vaginally administered medication e.g. isosorbide -5- mononitrate
- Those unwilling to participate in the trial
- Higher order cesarean section(more than three)

- **Methodology in details:**

All Patients will be informed about the study and will be included in the study after their approval and will be subjected to :

1- Consent :

Written consent will be obtained from the pregnant women who are included in the study after explanation of the study and its aims, for performing surgical evacuation for any remnants if needed .

2- Full History Taking :

- Name
- Maternal Age
- Obstetric history (Gravidity and parity)
- First day of last menstrual period
- Gestational Age
- Medical and surgical history
- Previous laparotomies and their types
- Previous Pregnancy complications
- History of smoking
- Pelvic pain

3- Clinical Examination :

- Height(in cm) and weight(in kg) measurements, BMI calculation
- Blood pressure measurement
- Bimanual Examinations (PV Examination)
- Previous scars analysis

4- Laboratory investigations :

- Preoperative and postoperative CBC
- Coagulation profile
- Kidney and liver functions

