- Blood sugar level
- Investigation:

All women will undergo Trans-abdominal or Trans-Vaginal Ultra-sonography during the routine examination to confirm the inclusion criteria of the study (gestational age and confirmation of missed abortion)

The patients will be allocated into 2 groups using computer-generated

randomization:

Group A (n =30) will receive **only** vaginal Misoprostol 800mcg (4 tablets Cytotec 200mcg)) every 3 hours to a maximum of two doses or until reaching cervical ripening or uterine contractions or bleeding assessed by the same doctor who made evaluation at the beginning.

Group B (n =30) will receive combined vaginal Misoprostol 800mcg (4 tablets Cytotec)) every 3 hours to a maximum of two doses or until reaching cervical ripening or start of uterine contractions or bleeding.

with Isosorbide-5-mononitrate (20 mg).

Effox 20 mg)once at the beginning with misoprostol until reaching cervical ripening or start of and uterine contractions assessed by the same doctor who made the evaluation at the beginning.

- **Intervention:**

Therapeutic intervention

No intervention

- **Does the research involve?**

Human participants

Biological samples/Tissues

Identifiable private data/Information

- **Potential risks:**

- 1- Complication of nitric oxide donor : Throbbing headache, postural hypotension , nausea, vomiting, sweating, flushing.
- 2- Complication of prostaglandin agent: abdominal pain, diarrhea, fever, rupture uterus.

allergic reaction, chills.

- **Confidentiality of data:**

- All study-related information will be stored secured at the study site.
- All participant information will be stored in locked file cabinets in areas with limited access.
- Participants, study information will be not released outside of the study without the written permission of the participant.

9- Study outcomes

- **Primary outcomes** (Most important measurable outcomes)

Induction to abortion interval: the Duration interval between the beginning of the induction and beginning of cervical ripening assessed by cervical examination(cervix become soft and start to dilate) and uterine contractions leading to complete expulsion of the abortus spontaneous and if cervical ripening isn't occur by maximum doses the investigators will make surgical evacuation.

and also the Number of the doses of misoprostol needed to complete expulsion (spontaneous or surgical)when prostaglandins used alone and when prostaglandins and a nitric oxide donor used together .

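### The dose-count primary outcome gives a woman evacuated after the drug failed the same score as a woman who expelled without surgery on the same number of doses, and no other outcome separates them

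*Protocol*

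**What the plan says.** Section 9 (Study outcomes) opens with "Primary outcomes (Most important measurable outcomes") and names two of them. The first is the induction-to-abortion interval. The second is the "Number of the doses of misoprostol needed to complete expulsion (spontaneous or surgical"), compared between misoprostol alone and misoprostol with the nitric oxide donor. The interval definition also carries the rule for drug failure: "if cervical ripening isn't occur by maximum doses the investigators will make surgical evacuation".

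Section 8, under Methodology in details, limits both arms to two misoprostol doses three hours apart, with the same earlier stops. Group A is dosed to two doses "or until reaching cervical ripening or uterine contractions or bleeding assessed by the same doctor". Group B is dosed to "a maximum of two doses or until reaching cervical ripening or start of uterine contractions or bleeding". The shorter text under Population of study gives Group A only ripening as an earlier stop ("Pfizer)every 3 hours to a maximum of two doses or until reaching cervical ripening") and names none for Group B ("every 3 hours to a maximum two doses with Isosorbide-5").

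The consent item in section 8 provides for a second route to surgery, "for performing surgical evacuation for any remnants if needed". The secondary outcomes in section 9 are adverse events only.

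**The concern.** The objective in section 6 is to compare therapeutic efficacy. In this setting the plainest sign that the drug did not work is that the uterus had to be emptied surgically. The dose count accepts surgical completion on the same footing as expulsion on the drug, so it does not register that event. Nothing else in the list of outcomes registers it as an event either. The interval definition mentions evacuation but gives an evacuated woman no value, and neither the number evacuated nor the number who expelled without surgery is an outcome.

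At stake is the reading of a primary result. Equal dose counts could be reported as equal efficacy when one arm needed more surgery. The analysis plan is not shown, but this is not a detail left to it: the protocol's own endpoint definition states that surgical completion counts.

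**Working it through.** **1. The plan's own figure, and why it is not at issue.** Section 10 plans on means of 10.7 h and 20.9 h with SDs of 12.8 and 13.8, 80% power and alpha 0.05 (taken as two-sided), using Student's t test. The difference is 20.9 − 10.7 = 10.2 h. With SD 13.8 the normal approximation gives n = 2 × (1.960 + 0.842)² × (13.8/10.2)² = 28.7, so 29 per group. The exact t calculation gives 30, with power 80.4%. The stated 30 reproduces. It concerns the interval; the dose count has no sample-size calculation.

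**2. Scores under the stated rules.** The maximum is two doses (section 8), and completion may be spontaneous or surgical (section 9).

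| Course | Score as written | Drug worked without surgery? |
|---|---|---|
| Expels completely after dose 1 | 1 | yes |
| Dose 1, then evacuated for remnants | 1 | no |
| Expels completely after dose 2 | 2 | yes |
| Dose 2, then evacuated for remnants | 2 | no |
| Unripe after dose 2, evacuated | 2 | no |

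Each score holds both successes and failures. This follows from the outcome wording and the cap alone, and does not depend on which text on stopping is followed.

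**3. Illustration of what the tie can hide.** The protocol gives no failure rates, so every share here is an assumption. Take 30 women per arm. In both arms 30% (9 women) expel after dose 1. Failure after two doses is 40% (12 women) in one arm and 10% (3 women) in the other. Two-dose expulsion is then 30% (9 women) and 60% (18 women).

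- Mean dose score, first arm: (9 × 1 + 21 × 2)/30 = 51/30 = 1.7.
- Mean dose score, second arm: (9 × 1 + 21 × 2)/30 = 51/30 = 1.7.
- Evacuations: 12/30 against 3/30, a gap of 30 percentage points that the dose score cannot show.

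In 3000 simulated trials of this kind, a Mann-Whitney test on the dose score as written rejected about 5% of the time, which is the alpha level. Ranking failure below two-dose expulsion raised this to about 34%. A direct comparison of failure proportions (normal approximation) has about 78% power: the mean proportion is 0.25, the null standard error √(2 × 0.25 × 0.75/30) = 0.1118, the alternative standard error √((0.4 × 0.6 + 0.1 × 0.9)/30) = 0.1049, and (0.30 − 1.96 × 0.1118)/0.1049 = 0.77, so power is 0.78.

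Varying the assumed failure in the first arm from 30% to 50%, against 10% in the other:

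| Assumed failure | Dose score as written | Failure ranked worst | Failure proportions |
|---|---|---|---|
| 30% v 10% | about 5% | 18% | 49% |
| 40% v 10% | about 5% | 34% | 78% |
| 50% v 10% | about 5% | 49% | 94% |

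The dose score stays at alpha by construction, because both arms were given the same one-dose share. The table shows the mechanism and does not forecast this trial.

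**The case against.** The best defence has three parts. First, the main failures are not flattered: under the only failure rule in section 9, a woman unripe after two doses scores 2, the worst value there is. Second, the objective is ripening, ripening is one of the dosing stops, and so the split between one and two doses says something about early response and misoprostol exposure. Third, counting surgical completion keeps every randomised woman in the comparison.

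The first two parts stand and limit the point. A reader might infer that the outcome rewards failure. For the main group it does not; it ties failure with late success at the ceiling. Only a woman evacuated after a single dose gets the better value, and the protocol does not say how often that happens or in which arm. Nor is the dose count worthless. What it cannot do is measure expulsion without surgery. The third part is true, but an ordered outcome with a failure category keeps every woman in as well.

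A reader might also infer that the stopping rules differ by arm and could themselves create a dose difference, because the Population of study text names an earlier stop for Group A and none for Group B. The documents do not support this. Methodology in details gives both arms the same stops, and the shorter text omits stops for Group B without denying them. This is a wording inconsistency to tidy.

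**Conclusion.** The point holds as a defect in a stated primary outcome. Drug failures and drug successes share a score at both one and two doses, and no other outcome in the protocol records evacuation or complete expulsion without surgery. Arms with equal dose counts could therefore differ in drug failure with no stated outcome to show it. It should be fixed.

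Its size and direction are unknown. They depend on how many women are evacuated in each arm, which the protocol does not give, and the figures in the illustration rest on assumed shares. If evacuation is equally common in both arms, the tie conceals no difference in failure.

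Two further inferences are not supported. The sample size is not affected, since it was set on the interval and reproduces. The tie also does not require evacuation to be triggered at a fixed time. Such a rule would change care, because section 9 calls for evacuation when the cervix has not ripened, not when a woman with a ripe cervix is still expelling. Scoring surgery separately is enough.

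**What to change.** In section 9, delete the parenthesis that admits surgical completion. Define the outcome in all randomised women as three ordered categories:

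1. complete expulsion without surgery after one dose;
2. complete expulsion without surgery after two doses;
3. surgical evacuation for any reason (failure, the worst category).

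Report the count in each category by arm. Within the third, show evacuation for non-ripening separately from evacuation for remnants.

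As tidying only, make the stopping text under Population of study match Methodology in details, which is the same in both arms. Do not add a clock-triggered evacuation rule.

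The cost is a change of wording in sections 8 and 9 and one or two extra fields on the patient sheet (whether evacuated, and why). No extra patients are needed. Results may look less favourable, because evacuated women will count as failures.

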Therapeutic abortions, as well as spontaneous miscarriages, can lead to a variety of complications. Most complications are considered minor such as pain, bleeding, infection, and post-anesthesia complications, while others are major, namely uterine atony with subsequent hemorrhage, uterine perforation, injuries to adjacent organs (bladder or bowels), cervical laceration, failed abortion, septic abortion, and disseminated intravascular coagulation (DIC).(**Carlsson, et al. 2018**)

Cervical ripening means thinning, softening and opening of the cervix. Various pharmacological& non pharmacological methods are available for cervical ripening each having its own advantages& disadvantages.(**Moustafa, et al. 2019**)

Misoprostol is a synthetic prostaglandin E1 analogue which was originally developed to prevent non-steroidal anti-inflammatory drugs related gastric ulcers. However it has been used for various other indications in obstetrics and gynaecology.(**Anderson, et al. 2009**)

Nitric oxide is a potent inflammatory intercellular mediator and signaling molecule. Nitric Oxide causes relaxation of smooth muscle that induces vasodilatation of both arteries and veins causing venous pooling of the blood. It was known for its effect as an endothelium-derived relaxing factor and a primary regulator of blood pressure. Several recent studies have shown that it is involved in several aspects of female reproductive physiology, including the process of cervical ripening. Nitric oxide is less effective than prostaglandin analogues, but has fewer adverse effects (**Mousioli, et al. 2013**).

There is an additive effect of the cervical ripening effects of nitric oxide donors and that of prostaglandins. The combination therapy allows a small dose of

nitric oxide donor to be given in combination with a small dose of prostaglandin to affect the cervical ripening. The advantage of such strategy is reducing the side effects associated with larger doses of either agent used alone(Arteaga et al. 2005).

6. Objectives:

The aim is to compare the therapeutic efficacy of prostaglandins when they used alone versus a combination therapy of prostaglandins and isosorbide-5-mononitrate to induce cervical ripening and effacement for induction of the first trimester missed abortion .

7. Study Design:

- Randomized Clinical Trial

8. Study Methods

- Population of study

All women who had first trimester missed abortion will be asked to participate the study

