- **Secondary outcome parameters** (other outcomes to be assessed)

Association between adverse events that increased or newly discovered when prostaglandins and a nitric oxide donor used together such as severe bleeding , headache, abdominal pain, pelvic pain, sever hypotension , backache, fever, nausea and vomiting .

10- Sample size

Sample size calculation was done using the comparison of induction to abortion interval in women with missed first trimesteric abortion treated with vaginal misoprostol combined with isosorbide mononitrate compared to those treated with misoprostol alone. As reported in previous publication (***Yehia and El ansary H 2020.***),, the mean \pm SD of induction to abortion interval in combined group was approximately 10.7 ± 12.8 h, while in misoprostol alone group it was approximately 20.9 ± 13.8 h. Accordingly, the investigators calculated that the minimum proper sample size was 30 participants in each group to be able to reject the null

hypothesis with 80% power at $\alpha = 0.05$ level using Student's t test for independent samples. Sample size calculation was done using PS Power and Sample Size Calculations software, version 3.0.11 for MS Windows (William D. Dupont and Walton D., Vanderbilt University, Nashville, Tennessee, USA).

11- Statistical analysis

The collected data using patient sheet form will be coded, entered on Excel sheet and analyzed using statistical package for social sciences (SPSS) Using appropriate statistical test, with a p value less than 0.05 considered as statistically significant, P value more than 0.05 Insignificant.

A descriptive statistics will be done using frequency distribution table, graphs, means, standard deviations, median and range, or frequency and percentage.

12- Source of funding:

- Faculty of Medicine, Cairo University
- Other sources:

Please specify: **Self-funding**

13- Time plan:

- When to start march 2021
- When expected to finish September 2021
- When to publish?

14- References:

- ❖ Anderson, J., E. Gouk, L. Young, L. Turnbull, G. et al(2009). ("P420 A randomised controlled trial of oral versus vaginal misoprostol for medical management of early fetal demise)." *International Journal of Gynecology & Obstetrics* **107**: S533-S533.

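### The only safety outcome is worded as adverse events that rise or newly appear with the combination and names no comparator, so equal or lower event rates fall outside it as defined

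*Protocol*

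**What the plan says.** Section 9 of the protocol, Secondary outcome parameters, has one entry: "Association between adverse events that increased or newly discovered when prostaglandins and a nitric oxide donor used together", with the examples "such as severe bleeding , headache, abdominal pain, pelvic pain, sever hypotension , backache, fever, nausea and vomiting". That is nine events if nausea and vomiting are counted separately. The list is open, but the opening condition applies to all of it.

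Other places that bear on this:

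- **Background, last paragraph.** On combining a nitric oxide donor with a prostaglandin: "The advantage of such strategy is reducing the side effects associated with larger doses of either agent used alone". The sentence before it ties this to small doses of both agents.
- **Section 6, Objectives.** "The aim is to compare the therapeutic efficacy of prostaglandins when they used alone versus a combination therapy". Safety is not mentioned.
- **Section 8, group descriptions.** Group A "will receive only vaginal Misoprostol 800mcg (4 tablets Cytotec 200mcg)(Pfizer)every 3 hours to a maximum of two doses". Group B has the same misoprostol dose, interval and maximum, plus isosorbide-5-mononitrate.
- **Section 8, Potential risks.** For the donor: "Throbbing headache, postural hypotension , nausea, vomiting, sweating, flushing". For misoprostol: "Complication of prostaglandin agent: abdominal pain, diarrhea, fever, rupture uterus", then allergic reaction and chills.
- **Section 11.** A general rule only: an appropriate test at p < 0.05, with descriptive statistics. It has no separate rule for adverse events.

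**The concern.** An outcome should be fixed before the data are seen. Here, membership depends on the result, because whether an event has gone up or is new can be judged only once the groups have been compared. It is also unclear what the comparison is with: Group A, the woman's own state before treatment, or published experience. The dose-count outcome in the same section does name both regimens; the safety outcome does not.

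If the sentence is followed as written, two things happen. Events that are higher in Group B by chance enter the safety result and look like added harm. Events that are equal or lower in Group B are outside the outcome, so a tolerability benefit would have no defined place in the report. That sits poorly with a background that offers fewer side effects as the reason to combine the two drugs.

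**Working it through.** **Inputs.** The 30 women per group come from section 10. The protocol gives no adverse event rates, so the rates below (2% to 50%) are assumptions.

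**The plan's own figure.** The safety outcome has none. The 30 per group rests on the primary outcome and reproduces: difference 20.9 − 10.7 = 10.2 h, SD 13.8 h, two-sided α = 0.05 (assumed, as sidedness is not stated) and 80% power with the t test give 29.7, rounded up to 30; power at 30 is 80.4%. It is used here only as the group size.

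**Literal rule, modelled.** An event qualifies if its observed count in Group B exceeds that in Group A. An event that is new in Group B (none in A, at least one in B) is a special case.

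**No true difference.** Let A and B be independent Binomial(30, p) counts with probabilities f(·). By symmetry,

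P(B > A) = [1 − P(A = B)] / 2, where P(A = B) = Σ f(k)².

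The mean apparent excess among qualifying events is

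E[(B − A)/30 | B > A] = Σ over b > a of ((b − a)/30) f(a) f(b), divided by P(B > A).

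| Assumed rate p | P(A = B) | P(B > A) | Mean apparent excess given B > A | Expected number of 9 events qualifying |
|---|---|---|---|---|
| 2% | 0.419 | 0.290 | 4.3 points | 2.6 |
| 5% | 0.246 | 0.377 | 5.7 points | 3.4 |
| 10% | 0.174 | 0.413 | 7.3 points | 3.7 |
| 20% | 0.129 | 0.436 | 9.4 points | 3.9 |
| 30% | 0.112 | 0.444 | 10.6 points | 4.0 |
| 50% | 0.103 | 0.449 | 11.4 points | 4.0 |

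Example at 10%: (1 − 0.174)/2 = 0.413, and 9 × 0.413 = 3.7. The last column gives all nine events the same rate, which is only a convenience. The true excess is 0 in every row.

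**A true reduction.** If the combination halved an event from 40% to 20%, P(B > A) = 0.031; from 50% to 25%, P(B > A) = 0.015. Under the literal rule, such an event would fall outside the outcome in about 97% and 98.5% of trials.

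**The lists side by side.** Six events named under Potential risks are absent from the outcome's examples: sweating and flushing (donor), and diarrhea, uterine rupture, allergic reaction and chills (misoprostol).

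**The case against.** The strongest reply is that this is loose English, not a selection rule. No section says to keep an event only if Group B exceeds Group A. The sentence names its events in advance and can be read as events that may rise or newly appear with the combination, which is an ordinary directional safety concern. An increase can be judged only against Group A, so the events must be recorded in both groups. Section 11 covers all collected data, with frequencies and percentages, and sets no one-sided rule.

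Much of this stands. A reader might infer that the trial cannot show a reduction, that lower event rates will be discarded, or that the investigators in fact choose events by result. The documents do not support those readings: nothing prevents a two-group table of the named events, and such a table would show a fall. What remains is that the protocol does not say this table is the outcome, and the sentence defining the outcome says something narrower.

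A reader might also infer that the outcome flatly contradicts the background rationale. It does not. That rationale concerns small doses of each agent against larger doses of either alone, whereas both groups here have the same misoprostol dose and maximum, and the stated aim is efficacy. A reduction could arise only through fewer doses, since dosing may stop early, or through the added agent. How the small-dose rationale relates to the regimens is a separate matter for the sponsor to reconcile.

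The omitted events are a lesser point: the list is open and already includes effects of both drugs. The size of the chance effect depends on the literal reading and on assumed rates; severe bleeding and severe hypotension may be rare, which is why the range starts at 2%. The choice of test and interval may properly be left to a SAP. The outcome definition is set in this protocol.

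**Conclusion.** The point holds as a defect of definition. The only safety outcome is conditional on the direction of its own result and names no comparator. Followed literally, it gives a one-directional account of safety. With 30 per group and equal true rates assumed between 2% and 50%, 29% to 45% of events with no true difference would qualify, with a mean apparent excess of about 4 to 11 percentage points. These figures illustrate the literal reading under assumed rates and do not predict what this trial will report.

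The wording should be corrected, but the sample size, the primary outcome and its analysis are untouched. Rewording will not make the trial strong on safety: at 30 per group, power would be about 39% for 40% against 20% and about 52% for 50% against 25% (assumed rates). That is a further reason to report every listed event in both groups.

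**What to change.** Replace the secondary outcome sentence in section 9 with: *the number and proportion of women in each group (misoprostol alone; misoprostol plus isosorbide mononitrate) with each of the following adverse events, recorded in the same way in both groups and compared whatever the direction of the difference.*

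Keep the present list and add the events already named under Potential risks in section 8: diarrhea, chills, sweating, flushing, allergic reaction and uterine rupture. The form of the comparison can be left to the SAP.

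The cost is one reworded sentence and a few more lines on the patient sheet. No additional women or visits are needed, and no dose or clinical rule changes.

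### Gestational age and parity are recorded for every woman, but the only comparison named is an unadjusted t test: prespecifying them as covariates is a cheap, conditional gain in precision

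*Protocol*

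**What the plan says.** - **Protocol, section 10 (Sample size).** The calculation takes the interval "in combined group was approximately 10.7 ± 12.8 h" and "in misoprostol alone group it was approximately 20.9 ± 13.8 h". It concludes that "the minimum proper sample size was 30 participants in each group" for 80% power, at the 0.05 "level using Student's t test for independent samples". No covariate enters.
- **Protocol, section 11 (Statistical analysis).** No test or model is fixed for any outcome: "Using appropriate statistical test, with a p value less than 0.05 considered as statistically significant".
- **Protocol, section 8 (Inclusion criteria).** The eligible range is "Gestational age first trimester of pregnancy (between 5-13 weeks"; no limit on parity is listed.
- **Protocol, section 8 (Full History Taking and Investigation).** The history taken from all patients includes "Obstetric history (Gravidity and parity" and gestational age. Ultrasound also checks gestational age in all women. Both steps are listed ahead of allocation.
- **Protocol, section 8 (allocation).** Randomisation is computer-generated; no stratification is stated.
- **Protocol, section 9 (Primary outcomes).** The interval can be cut short, because women whose cervix has not ripened after the maximum doses go to surgical evacuation.

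**The concern.** Women between 5 and 13 weeks, of any parity, may differ a good deal in how quickly the cervix ripens and the pregnancy is expelled. That is a clinical presumption; the protocol gives no figure for it. If it is true, the variation due to these two factors stays in the error term of an unadjusted comparison, and the confidence interval for the treatment effect is wider than it need be.

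The data to remove that variation are already collected. The trial is small, and on the larger of its two planning SDs it has little power to spare. No allowance for dropout is stated. Because section 11 leaves the method open, there is a second point at stake: covariates that are not named in advance could be chosen after the results are seen.

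**Working it through.** **Inputs from section 10.** Means 20.9 h and 10.7 h, so the difference is 20.9 − 10.7 = 10.2 h. SDs 13.8 h and 12.8 h; pooled SD = √((12.8² + 13.8²)/2) = 13.31 h. n = 30 per arm, α = 0.05. Sidedness is not stated. Two-sided is assumed, because one-sided calculations (normal approximation) give only 20 to 23 per arm.

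**Step 1: reproduce the stated size.** With the exact non-central t calculation, 80% power needs 30 per arm at SD 13.8, 28 at the pooled SD and 26 at SD 12.8. The stated 30 is reproduced with SD 13.8. At that SD the standard error of the difference is 13.8 × √(2/30) = 3.56 h, the non-centrality is 10.2/3.56 = 2.86, and power on 58 degrees of freedom is 80.4%. With the pooled SD, power at 30 per arm is 83.1%.

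**Step 2: adjust for two covariates.** Let R² be the share of within-arm variance in the interval that gestational age and parity explain together. It is not in the documents; the range 0 to 0.30 is an assumption. Three things change:
- the residual SD becomes 13.8 × √(1 − R²);
- degrees of freedom fall from 58 to 56;
- chance imbalance in the covariates inflates the expected variance by about (N − 3)/(N − 3 − 2) = 57/55 with N = 60.

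The ratio of adjusted to unadjusted standard error is therefore √((1 − R²) × 57/55).

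| Assumed R² | SE ratio | SE (h), SD 13.8 | Power, SD 13.8 | Power, SD 13.31 |
|---|---|---|---|---|
| Unadjusted | 1 | 3.56 | 80.4% | 83.1% |
| 0 | 1.018 | 3.63 | 78.9% | 81.7% |
| 0.05 | 0.992 | 3.54 | 80.9% | 83.6% |
| 0.10 | 0.966 | 3.44 | 83.0% | 85.6% |
| 0.20 | 0.911 | 3.24 | 87.1% | 89.3% |
| 0.30 | 0.852 | 3.03 | 91.0% | 92.9% |

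**Step 3: break-even.** The standard errors are equal when (1 − R²) × 57/55 = 1, that is R² = 1 − 55/57 = 0.035. Below this, adjustment loses slightly. The largest loss, at R² = 0, is 80.4 − 78.9 = 1.5 points of power, or 1.8% in the standard error.

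**Step 4: does the linear model fit this endpoint?** The planning SD exceeds the mean in the combined arm (12.8 against 10.7) and is about two thirds of it in the other (13.8 against 20.9), which suggests a skewed interval. Surgical evacuation also truncates it. The table shows the order of magnitude under a linear normal model; it does not predict the gain in a time-to-event model.

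**The case against.** The strongest objection is that the protocol commits to nothing here. The t test appears only as the basis of the sample size, section 11 names no test, and covariates are commonly left to a statistical analysis plan, which is not at hand. Sizing on an unadjusted test and adjusting later is ordinary practice. This stands, and it is why the point is an improvement and not a fault.

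Two stronger readings are tempting, and the documents support neither.

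- **That the planned comparison is biased or exposed to imbalance.** The chance that mean gestational age differs between arms by at least 0.5 SD is 2 × (1 − Φ(0.5/√(2/30))) = 0.053. If all of an R² of 0.10 to 0.30 belonged to gestational age, an imbalance of exactly 0.5 SD would move the difference by 0.5 × √R² × 13.8 = 2.2 to 3.8 h. But that is sampling error which the unadjusted standard error of 3.56 h already covers. Parity would also share the R², so the shift is on the high side. Randomisation keeps the unadjusted test valid.
- **That adjustment is sure to gain and costs nothing.** No prognostic strength is documented, and with 60 women two useless covariates cost about 1.5 points of power. Ignoring that penalty would put power at 84%, 88% and 92% for R² of 0.10, 0.20 and 0.30; the net figures are about one point lower each.

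It is also fair to object that a linear calculation does not describe a time-to-event analysis. In a hazard model, adjustment changes the quantity being estimated as well as its precision. That too stands, and limits the table to an indication.

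**Conclusion.** A minor efficiency point holds. The sample size is correct on its own inputs, and nothing in the protocol is wrong or contradictory on this matter. What it leaves unused is a likely but unproven gain: about 3 to 11 points of power if gestational age and parity explain 10% to 30% of the variance, and practically none near 3.5%. If they explain nothing, there is a loss of about 1.5 points.

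The conclusion rests on an assumed R², a two-sided 0.05 test, SD 13.8 h, all 60 women analysed, and a linear model. With the pooled SD the pattern is the same from a higher starting point. An analysis plan that already names these covariates would settle the matter.

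**What to change.** Add one sentence to section 11, or to the analysis plan, before the data are looked at. It should say that the primary comparison of the induction-to-abortion interval adjusts for gestational age in weeks (continuous) and parity, in whichever model is chosen to handle women who go to surgical evacuation. It should also say that the unadjusted result is reported as supporting. If that model is a time-to-event model, state whether the reported effect is conditional on the covariates. How parity is coded should be fixed in the same sentence.

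The cost is two degrees of freedom and the small possible loss of power shown above. No new data and no more women are needed, and the open wording of section 11 means that no existing text has to be contradicted.
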